6.5 Contour Evaluation, Treatment Planning, and Treatment Delivery

The experienced clinician will review and edit all contours for final approval and clinical use for HDR prostate radiotherapy planning and treatment. Treatment planning will be done in the usual fashion by the brachytherapy medical physicist using Oncentra prostate treatment planning software. The experienced clinician will review and approve the HDR brachytherapy treatment plan per institutional metrics and constraints. The HDR brachytherapy plan will be delivered to the prostate using an iridium-192 afterloader per standard operating procedure.

6.6 Post-treatment TRUS

Following treatment plan delivery, the bottom half of the interstitial prostate needles will be removed. TRUS images #3 will be obtained with better visualization of the anterior border of the prostate. These TRUS images represent the “ground truth” in terms of the location and outline of the prostate.

The interstitial implant will then be completely removed, and the patient will be transferred to recovery area.

6.7 Radiation Adverse Events

It is not anticipated that auto-contouring of the prostate would increase the risk of side effects of prostate HDR brachytherapy. The procedure may take longer overall, such as to obtain the post-brachytherapy TRUS, increasing the length of general anesthesia. This is not expected to pose an increased risk to participants beyond the usual total procedure time variations which occur in the real-world setting.

7. PARTICIPANT ASSESSMENTS

Patients with prostate cancer will be assessed in clinic for suitability for HDR prostate brachytherapy as a monotherapy, boost or salvage treatment per investigator discretion. No additional assessments are required for participation in this study.

8. DATA COLLECTION

Study Evaluation	Patient screening	New learner prostate contouring training session ¹	HDR Brachytherapy
	Within 90 days prior to registration		
REQUIRED PATIENT ASSESSMENTS			
Informed consent	X		
Diagnosis and staging information	X		
Oncologic history	X		
BRACHYTHERAPY			
New learner baseline contours		X	
Prostate_Learner_Image1			X
Prostate_Learner_Image2			X
Prostate_Clinician_Image2			X
Prostate_Clinician_Image3			X
Time to generate and edit contours			X
STUDY SURVEYS			
New learner baseline experience survey		X	
New learner contouring survey			X
Experienced clinician survey			X

¹The training session will only be performed one time prior to the first case in which the new learner participates.

9. STATISTICAL CONSIDERATIONS

9.1 Study Design/Endpoints

The primary objective of this study is to evaluate whether AI-assisted contours perform better than manual contours as measured by the Dice coefficient between the final contours used for treatment delivery versus the contours, either manual or AI-assisted, provided by the new learners. Patients will be accrued in one stage. Each patient will be assigned to a new learner and then randomized to manual versus AI-assisted contouring. The randomization will be stratified by new learner type: resident versus fellow/new attending.

The experienced clinician will be blinded to the randomization of the contouring method by the

new learner. The prostate contour generated by the new learner will then undergo review by the experienced clinician. The dice coefficient between the new learner prostate contour and the experienced clinician contour will be calculated. The experienced clinician will approve the prostate brachytherapy contours to be used clinically for HDR prostate radiotherapy planning and treatment.

[figure not shown]
9.2 Primary Objective

The primary objective of this study is to evaluate whether the addition of artificial intelligence can improve the quality of implanted prostate contours as measured by the Dice coefficient between the final contours used for treatment delivery versus the contours, either manual or AI-assisted, provided by the new learners. The Dice coefficient ranges between 0 and 1, where 0 indicates no match, and 1 indicates complete match.

9.3 Sample Size, Accrual Rate and Study Duration

The sample size of this study will be 36 patients.

Based on data from previous published work with the AI algorithm for HDR brachytherapy prostate contouring with the needles in place, we can assume a mean Dice coefficient of 0.87 for manual new learner contours (without AI) and a mean Dice coefficient of 0.92 for AI-assisted new learner contours ⁹. Using a standard deviation of 0.05, a one-sided alpha of 0.1, and a power of 0.9, a total of 27 patients will be needed for this study using a t-test. As each new learner will generate prostate contours for multiple patients in this study, the correlations among patients contoured by the same new learner need to be taken into account. Assuming an intra-cluster correlation of 0.15 and an average of 3 patients to be contoured by the same new learner in a given arm, the sample size will be inflated by 30% (36 analyzable patients) in order to maintain sufficient power. The maximum number of cases that a new learner can contour would be 10.

There are approximately 75 prostate brachytherapy patients that undergo HDR treatment of the whole gland in the Department of Radiation Oncology at Brigham and Women's Hospital. If about half agree to participate, we expect the study to take about 12 months to accrue.

This study does not include follow-up after HDR brachytherapy treatment delivery and termination of accrual.

Accrual Targets						
Ethnic Category	Sex/Gender					
	Females		Males		Total	
Hispanic or Latino	0	+	3	=	3	
Not Hispanic or Latino	0	+	33	=	33	
Ethnic Category: Total of all subjects	0	(A1)	+ 36	(B1) =	36 (C1)	
Racial Category						
American Indian or Alaskan Native	0	+	0	=	0	
Asian	0	+	3	=	3	
Black or African American	0	+	3	=	3	
Native Hawaiian or other Pacific Islander	0	+	0	=	0	
White	0	+	30	=	30	
Racial Category: Total of all subjects	0	(A2)	+ 36	(B2) =	36 (C2)	
	(A1 = A2)		(B1 = B2)		(C1 = C2)	

Note that this study is limited to patients with a prostate. There may be some patients who identify as female and were assigned male at birth with a prostate eligible for this study not explicitly stated in the accrual targets.

9.4 Stratification Factors

We will introduce a stratification factor by training category of new learner: 1. resident versus 2. fellow/new attending.

9.5 Interim Monitoring Plan

This is not a therapeutic trial and the standard U-net algorithm generating a prostate auto-contour during HDR prostate brachytherapy will be used by the new learner. All brachytherapy contours will undergo review by the experienced clinician for clinical approval prior to patient treatment in the usual fashion of an academic teaching center. As such, there will not be planned interim safety monitoring.

9.6 Analysis of Primary Endpoints

The participant cohort are patients undergoing whole gland prostate HDR brachytherapy for monotherapy, boost or salvage radiation at the Brigham and Women's Hospital/Dana-Farber Cancer Institute Department of Radiation Oncology.

The primary endpoint of the study is the Dice coefficient [0: no match, 1: complete match]

between the final clinically approved prostate contours versus the manual or AI-assisted contours provided by the new learner. The primary objective is to evaluate whether the addition of artificial intelligence can improve the quality of implanted prostate contours as measured by Dice coefficient. As multiple patients will be contoured by the same new learner on this study, the Dice coefficient will be compared between the two groups using a mixed-effect model with new learner as a random effect to account for the potential variability of contouring among the new learners.

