2. OBJECTIVES

2.1 Study Design

This is a Phase II prospective study evaluating a deep learning AI algorithm for auto-contouring of the prostate during HDR prostate brachytherapy with the needles in place by new learners. The study will be conducted with a randomized design. Each patient will be assigned to a new learner and then randomized to manual versus AI-assisted contouring. The randomization will be stratified by new learner type: resident versus fellow/new attending. The hypothesis is that AI-assisted learner contours will have improved Dice coefficients with respect to clinically approved contours compared with manual learner contours. All brachytherapy contours will undergo review by the treating radiation oncologist who is the experienced clinician for clinical approval prior to patient treatment. The experienced clinician will be blinded to the randomization. Clinicians will not be registered in OnCore.

DF/HCC Office of Data Quality will perform randomization. If the new learner of a case is a resident, then the "resident" randomization tab will be used for the randomization. If the new learner of a case is a fellow/new attending, then the "fellow/new attending" tab should be used to determine which arm the case goes to.

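### Is the primary analysis unsound because its model does not name learner type, the factor that stratifies the randomization?

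*Protocol*

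**What the plan says.** Protocol 9.1 states: "The randomization will be stratified by new learner type: resident versus fellow/new attending". Section 9.4 repeats it: "We will introduce a stratification factor by training category of new learner: 1. resident versus 2. fellow/new attending". Section 2.1 gives the mechanics: each learner type has its own randomization list, and the matching "tab should be used to determine which arm the case goes to".

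Section 9.6 describes the primary comparison: "the Dice coefficient will be compared between the two groups using a mixed-effect model with new learner as a random effect". The reason it gives is that one learner contours several patients, so contouring may vary between learners. Learner type appears neither there nor anywhere else as an analysis term, and no section rules it out.

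The sample size in 9.3 rests on "a one-sided alpha of 0.1, and a power of 0.9", mean Dice values of 0.87 and 0.92, and an SD of 0.05. For clustering it adds: "Assuming an intra-cluster correlation of 0.15 and an average of 3 patients to be contoured by the same new learner in a given arm".

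**The concern.** A factor that restricts the randomization is normally carried into the primary analysis. Stratified allocation balances the arms on that factor. If the analysis ignores it, the variation it explains stays in the error term, so the standard error is too large, the test conservative and some power lost. Here the trial has a single stratification factor, stated three times, and the one sentence that describes the primary model leaves it out. With only 36 patients, a loss of precision or a distorted type I error would matter, and adding the term would take one phrase.

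**Working it through.** **What 9.6 fixes.** It fixes the type of model and its random part. It does not list the fixed effects; even the arm appears only as the comparison being made. Reading it as arm plus a learner random intercept and nothing else is the least favourable reading for the plan, and it is the one tested below.

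**The plan's own sample size.** Inputs from 9.3: difference 0.92 − 0.87 = 0.05, SD 0.05, one-sided alpha 0.10, power 0.90.

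- Normal approximation: total = 4 × (1.2816 + 1.2816)² × (0.05/0.05)² = 26.28, so 27. A t-test with 13 + 14 patients has power 0.898.
- Design effect: 1 + (3 − 1) × 0.15 = 1.30, and 27 × 1.30 = 35.1, taken up to an even 36.

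The stated figures reproduce, and none depends on a learner-type term.

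**How large a type difference can be.** Total variance is 0.05² = 0.0025. The between-learner part is 0.15 × 0.0025 = 0.000375 and the residual part 0.85 × 0.0025 = 0.002125. Type is a property of the learner, so a type gap is part of the between-learner variance. With equal numbers of each type, a gap g contributes 0.25 × g². The largest gap compatible with the ICC is therefore 2 × √0.000375 = 0.0387. At that gap nothing is left over: 0.000375 − 0.25 × 0.0387² is about 0, so learners of the same type would be identical.

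**Best attainable precision.** Patients are randomized after assignment to a learner, so a learner can contribute to both arms and the learner effect can cancel from the arm contrast. With complete cancellation the SE is √(4 × 0.002125/36) = 0.01537. In equal-split settings at gaps 0, 0.03 and 0.0387, the model without type has a mean model SE of 0.01540 to 0.01589, already close to this floor.

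**Simulation of the two models.** REML random-intercept fits; 20,000 trials per setting and 24 settings; 36 patients; 12 learners × 3 cases, 6 × 6 and 4 × 9; equal and unequal type splits; permuted blocks of 4 within type. The 6 × 6 layout matches the average of 3 patients per learner per arm in 9.3. Layouts, splits, block size and gaps are assumptions. Change when learner type is added as a fixed effect:

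| Type gap | Model SE | Empirical SE | Power (points) |
|---|---|---|---|
| 0 | −0.1% to +0.1% | +0.05% to +0.16% | −0.1 to +0.1 |
| 0.02 | −0.3% to −1.1% | +0.1% to −0.2% | 0 to +0.2 |
| 0.03 | −0.7% to −2.7% | 0 to −0.8% | 0 to +0.5 |
| 0.0387 (limit) | −1.4% to −5.0% | −0.4% to −2.0% | +0.1 to +0.8 |

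The model without type has absolute bias of at most 0.0002, type I error 0.096 to 0.107 (Monte Carlo SE 0.002) and power 0.958 to 0.971. With type, type I error is 0.100 to 0.108.

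In a further simulation with 6 and 12 learners, the arm estimates from the two models correlated 0.988 to 0.998. Empirical SE showed no gain beyond Monte Carlo noise at gaps 0 to 0.02, and a gain of about 1.5% at 0.0387.

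**Why the model SE falls more than the empirical SE.** Part of the fall is optimism. For 12 × 3 at gap 0.0387, model against empirical SE is 0.01589 against 0.01608 without type (1.2% too small) and 0.01510 against 0.01577 with type (4.2% too small). For 6 × 6 at the same gap, the shortfall goes from 1.4% to 3.0%. The value 0.01510 lies below the floor of 0.01537, so it cannot be a true gain in precision.

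**The case for a change.** The strongest case for the concern is that 9.6 does not leave the model wholly open. It names the method and one term, yet omits the only factor the trial stratifies on. The random effect is also an imperfect substitute: it absorbs a type difference only when the between-learner variance is estimated above zero. At ICC 0.15 and 36 patients, that estimate falls to zero in about 22 to 24% of trials, and the analysis then becomes an unadjusted comparison.

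The factual part stands: learner type is not named. The zero-variance argument is also correct, but those trials are already included in the simulated averages, so it explains the small gain without enlarging it. Stratified blocks also keep the arms nearly balanced on type in every trial, so even then the arm estimate is not biased.

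A type gap above 0.0387 would mean an ICC above the planned 0.15. A second simulation (3,000 trials per setting) took the gap to 0.05: power went from 0.962 to 0.964 with 6 learners and from 0.947 to 0.956 with 12, above 0.90 either way. Across that simulation, type I error was 0.097 to 0.112 without the term and 0.102 to 0.116 with it.

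**Conclusion.** The concern does not hold. The protocol states nothing wrongly and does not contradict itself: 9.4 describes the allocation, 9.6 describes how clustering by learner is handled, and 9.6 excludes no fixed effect. A full covariate list is ordinary content for a statistical analysis plan, so its absence here is not a defect. Taken literally, the stated model still gives a sound result, being essentially unbiased, with type I error near 0.10 and power above the planned 0.90.

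Adding learner type is a matter of preference. It is worth nothing measurable at gaps up to 0.02. It is worth at most about 2% in empirical SE and 0.8 power points at the limiting gap, where all between-learner variation would have to be type.

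This rests on the SD and ICC in 9.3, on normally distributed learner effects, and on assumed learner numbers, type splits, gaps and block size, none of which the protocol gives.

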9.7 Analysis of Secondary Endpoints

- Descriptive statistics will be used to characterize measurement of contouring time-to-complete needed to generate and edit manual vs AI-assisted contours for a new learner. The contouring time will be compared between the two groups using the t-test.
- Likert scale data from the new learner and experienced clinician surveys will be reported using mean and standard deviation and compared between the two arms using a t-test¹⁰.
- The percentage of correct predictions by the experienced clinician of whether the prostate was contoured with or without AI-assistance will be reported along with 90% exact binomial confidence interval.
- The prostate contour quality score of the new learner's prostate contour presented to the experienced clinician during radiotherapy plan development with and without AI-assistance, described using descriptive statistics and compared using the chi-squared test.

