2.3 Secondary Objectives

- To measure contouring time-to-complete needed to generate and edit manual vs AI-assisted contours for a new learner.
- To evaluate the subjective impressions of AI or manual contours by the new learner based on survey responses.
- To evaluate the subjective impressions of AI or manual contours by the experienced clinician based on survey responses.
- To calculate Dice coefficients of expert clinician contours between TRUS images with implanted needles and TRUS images after removal of bottom needle rows.

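### Section 9.7 compares the clinician's contour quality score by chi-squared, which ignores the order of the grades; an ordinal test would serve better if the score has three or more grades

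*Protocol*

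**What the plan says.** The item is the last bullet of Protocol 9.7: "The prostate contour quality score of the new learner's prostate contour presented to the experienced clinician during radiotherapy plan development", which is to be compared "with and without AI-assistance, described using descriptive statistics and compared using the chi-squared test". The protocol does not state how many grades the score has, how they are worded, or which form records it. Section 2.3 does not list the score as an objective of its own, and the data collection table in section 8 shows no separate instrument for it.

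The same section treats the neighbouring measures differently. Contouring time is compared by t-test. For the surveys, "Likert scale data from the new learner and experienced clinician surveys will be reported using mean and standard deviation", again with a t-test between arms.

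Three other statements bear on the point. On the rater, section 2.1 says: "The experienced clinician will be blinded to the randomization". On direction: "The hypothesis is that AI-assisted learner contours will have improved Dice coefficients". On size, section 9.3 says: "The sample size of this study will be 36 patients". Section 9.3 also says that correlation among patients contoured by the same learner has to be taken into account.

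**The concern.** A quality score has a better and a worse end. The trial asks whether AI assistance moves contours towards the better end. Pearson's chi-squared gives the same p-value however the grades are ordered. It spreads its sensitivity over k−1 degrees of freedom, covering every kind of difference between the arms, most of which are not of interest. Of the three between-arm comparisons in 9.7 (time, Likert items, quality score), only this one uses a test without direction.

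What is at stake is a clinical reading of contour quality by a blinded expert, which would naturally be set beside the Dice result. With about 18 patients per arm, the planned test could miss a real upward shift that an ordinal test would detect. The test also takes no account of learner, which the primary analysis in 9.6 does.

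**Working it through.** **1. The plan's own figure.** No power is stated for the quality score, so the only figure to reproduce is the primary sample size. Section 9.3 gives means of 0.87 and 0.92, and says: "Using a standard deviation of 0.05, a one-sided alpha of 0.1, and a power of 0.9". The standardised difference is (0.92 − 0.87)/0.05 = 1.0. The normal approximation gives 2 × (1.2816 + 1.2816)² / 1.0² = 13.1, so 14 per arm. The exact t-test has power 0.898 with 13 + 14 = 27 patients, which matches the stated 27. The design effect is 1 + (3 − 1) × 0.15 = 1.30, and 27 × 1.30 = 35.1, rounded up to 36. The figure reproduces. At 1:1 allocation (assumed, as the ratio is not stated), this gives 18 per arm.

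**2. A worked table.** Take five grades, worst to best, with invented counts: manual 2, 4, 6, 4, 2 and AI-assisted 0, 2, 4, 6, 6.

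- Column totals are 2, 6, 10, 10, 8, so the expected counts in each arm are 1, 3, 5, 5, 4.
- Chi-squared = 2 × (1²/1 + 1²/3 + 1²/5 + 1²/5 + 2²/4) = 2 × 2.733 = 5.47 on 4 df, p = 0.24. Shuffling the columns leaves it unchanged.
- Rank-sum: U = 230 against a null mean of 18 × 18/2 = 162. The tie-corrected variance is (18 × 18/12) × (37 − 2700/1260) = 941.1, with square root 30.7. So z = 68/30.7 = 2.22 and two-sided p = 0.027.
- The size of the shift is 230/324 = 0.71, the chance that an AI-assisted contour scores higher than a manual one, with ties counted half.

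**3. Power.** A graded score was simulated from a normal latent variable shifted upward in the AI arm (5,000 runs per setting, 18 per arm, independent patients, both tests two-sided at 0.10). Assumed manual-arm grade probabilities were (.5, .5), (.3, .4, .3), (.2, .3, .3, .2) and (.1, .2, .4, .2, .1). The two-sided 0.10 level is also an assumption; 9.7 sets no level for this item.

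| Grades | Shift 0.5 SD: chi-squared / rank-sum | 0.8 SD | 1.0 SD | Loss, points |
|---|---|---|---|---|
| 2 | 0.360 / 0.360 | 0.603 / 0.603 | 0.744 / 0.744 | 0 |
| 3 | 0.306 / 0.374 | 0.569 / 0.663 | 0.723 / 0.817 | 6.8 to 9.4 |
| 4 | 0.275 / 0.391 | 0.529 / 0.703 | 0.696 / 0.859 | 11.6 to 17.4 |
| 5 | 0.230 / 0.399 | 0.477 / 0.717 | 0.661 / 0.867 | 16.9 to 24.0 |

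A skewed five-grade distribution (.05, .1, .25, .4, .2) gave 0.452 / 0.692 at 0.8 SD.

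A different model, a proportional-odds shift with odds ratio 3.5, gave 0.57 / 0.57 with two grades, 0.51 / 0.62 with three, 0.44 / 0.61 with four and 0.42 / 0.64 with five. A separate run of that model with four grades gave 45% / 63%. Taking both models together, the losses are about 0, 7 to 11, 12 to 18 and 17 to 24 points.

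**4. Type I error.** With no shift, at nominal 0.10, chi-squared / rank-sum rejected in 0.128 / 0.128 (two grades), 0.106 / 0.101 (three), 0.104 / 0.103 (four) and 0.096 / 0.108 (five) of runs. Chi-squared is no worse than the alternative.

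**5. Cell sizes.** The average expected count per cell is 18/k: 6.0, 4.5 and 3.6 for three, four and five grades. With manual-arm probabilities of (.25, .45, .30), the expected counts are 4.5, 8.1, 5.4, so one in three is below 5. With (.10, .20, .40, .30) they are 1.8, 3.6, 7.2, 5.4, so half are.

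**The case against.** The best defence is that the number of grades is unknown. Section 9.7 sends Likert data to a t-test and lists this score separately with chi-squared, which fits an intention to treat it as a category such as acceptable or not. With two categories chi-squared is a standard choice and loses nothing. This stands, and it makes the point conditional. It does not remove it, because a rank-sum test has the same power with two grades, so the change does no harm there.

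Several stronger readings are tempting, and the protocol does not support them:

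- *That this is the only blinded clinical rating.* It is not. Section 2.3 has a further objective: "To evaluate the subjective impressions of AI or manual contours by the experienced clinician based on survey responses". The same blinded clinician completes that survey, and its Likert data are compared by t-test.
- *That small cells make chi-squared invalid here.* Most expected counts fall below 5 only with about five grades, and the null simulations show no inflation beyond that of the rank-sum test.
- *That a significant result would leave the better arm unknown.* The planned descriptive statistics would show the direction.
- *That the stated hypothesis requires a directional test of this score.* The stated directional hypothesis concerns Dice. The aim of improving contour quality makes an ordered test the natural one, but the protocol sets no direction, level or power for this item.

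It is also fair to say that the simulated patients were independent, whereas 9.3 assumes an intra-cluster correlation of 0.15 within learner. The absolute powers are therefore not those of this trial; the comparison between the tests is what they are used for. A plain rank-sum or trend test ignores learner just as chi-squared does.

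**Conclusion.** The point holds in a limited form. The protocol names a test that discards the order of a quality score, although the aim is to improve quality and the adjacent Likert data get a test that uses order. With three or more grades the planned test is the weaker one, modestly with three and substantially with four or five; with two grades there is no loss. These sizes rest on 1:1 allocation, a two-sided 0.10 level, independent patients, and grade distributions and effects that the protocol does not supply.

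This is a cheap improvement to a secondary comparison, not a flaw in the trial's main inference, because the primary mixed-model analysis of Dice in 9.6 does not depend on it.

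**What to change.** In 9.7, replace the chi-squared test for the contour quality score with a comparison that uses the order of the grades. The preferred choice is a proportional-odds (cumulative logit) model with new learner as a random effect, which also brings this item into line with 9.3 and 9.6. If that model cannot be fitted with 36 patients, use a Wilcoxon rank-sum or exact trend test. Report the direction and size of the shift (a common odds ratio, or the probability that an AI-assisted contour scores higher), and keep the table of counts per grade as description.

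The cost is one sentence, best changed before results are seen. It needs no new data, patients or procedures. The one statistical downside is lower sensitivity to a pure difference in spread, where AI contours are both more often best and more often worst; the retained counts per grade would still show such a pattern.
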